3.2. Study Endpoint(s)

Endpoints will be further defined in subsequent sections. Unless otherwise specified, time-to-event endpoints will be calculated from the date of HSC infusion. If a patient received more than one HSCT, the time of the last HSC infusion immediately preceding infusion with BPX-501 will be the transplant date.

Primary Endpoint:

Event-Free Survival (EFS) at 180 days. Events are defined as the first occurrence of either transplant-related mortality (TRM) for non-malignant patients or non-relapse mortality (NRM) for malignant patients, severe GvHD (Grade 2-4 acute organ GvHD or extensive/moderate-severe chronic GVHD), and life-threatening infections (Grade 4).

NB: In the BPX-501 protocols, the terminology 'extensive' chronic GvHD was used. For the purposes of the primary analysis and for the rest of this SAP, extensive chronic GvHD will be defined as moderate or severe chronic GvHD. 'Overall' chronic GvHD or chronic GvHD without a qualifier will be interpreted as mild, moderate or severe chronic GvHD.

The following secondary endpoints are in the BP-004 protocols, although additional endpoints and analyses are described below in subsequent sections of this document.

Secondary Endpoints:

- (i) Transplant-Related Mortality (TRM) in patients with non-malignant diagnoses or Non-Relapse Mortality (NRM) in patients with malignant diagnoses at 100 and 180 days
- (ii) Cumulative incidence and severity of acute GvHD (any Grade 2-4 or Grade 3-4) as well as overall and moderate-severe chronic GvHD at 180 days.
- (iii) Time to resolution of acute GvHD after administration of rimiducid
- (iv) Immune reconstitution as determined by T cell subsets up through 180 days
 - a. Absolute CD3 count
 - b. Absolute CD4 count

- c. Absolute CD8 count
- (v) Time-to-immune reconstitution defined by CD3 count > 500 cells/uL; CD4 count > 200 cells/uL; CD8 count of 200 cells/uL
- (vi) Disease-Free/chronic GvHD Survival (DFGS) defined as the first of either disease recurrence, death from any cause, or chronic GVHD
- (vii) Disease status within the following disease indications at 180 days:
 - a. Primary immune disorders as determined by CD3 T cell count ≥ 500 cells/uL and normal levels of IgA and IgM
 - b. Haemoglobinopathies as determined by incidence of RBC transfusion independence for 8 consecutive weeks and untransfused haemoglobin of ≥ 8.5 g/dL

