6.2.2. Missing Data and Handling of Dropouts

Unless otherwise specified, missing data will not be imputed for efficacy variables. For subjects who withdrew from the study prior to study completion, all data attained up to the point of discontinuation will be listed and included in data summaries. Patients will be censored at the time of their last documented study visit prior to or at the time of study withdrawal.

The term missing date refers to a completely missing date or to a partial date where month, day or year are missing. Unless otherwise stated, the handling of partial missingness of dates will impute using midpoint values. That is, missing days will be imputed as the 15th of the month and

missing months will be imputed as July 1st, unless a more suitable value can be imputed based on study or treatment start and end dates.

If an adverse event (AE) resolution date is completely missing, the duration (ongoing/resolved status) will be checked before imputing a date, noting when the AE started in relation to study treatments. If the ongoing flag is missing, then it is assumed that the AE is still present (i.e., do not impute a date).

Adverse event relationship missing: If the relationship for an adverse event is not recorded, it will be reported as missing in the presentation of listings and summaries of incidence results. Assessments of relatedness to AP1903/rimiducid should only apply for AEs which occur on or after the date of first rimiducid dose.

Adverse event severity missing: If the severity of an adverse event is missing, the severity will be assumed to be missing when summarizing data. Missing information will be reported as missing in the subject listings.

Non-study medication (concomitant medications, steroids) start and stop dates missing: If the start and/or stop dates of non-study medication use are incomplete or missing, the use will be assumed to be concomitant, unless the incomplete date information clearly indicates that the use stopped prior to the on-study-date. Missing or incomplete information will be reported as missing/incomplete in the subject listings.

For pharmacology and pharmacokinetic data, the following rules will be applied if there are values that are below the limit of quantitation (BLQ) or if there are missing values (e.g., no result [NR]) in a plasma concentration data series to be summarized.

- For the calculation of summary statistics, BLQ values will be set to zero.

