6.2.3. Baseline Definition

For this study, the patient begins study treatment on the day of hematopoietic stem cell transplantation (HSCT) defined as Day 0 in the protocol and study Day 1 for analysis. It is noted that the study schedule from the protocol refers to the reference date as Day 0. For reporting purposes, CDISC standards will be used, referring to the first day as Day 1.

If a patient received multiple HSCTs, the date of HSCT which occurred immediately before administration of BPX-501 will be considered study Day 1.

For all endpoints requiring a baseline reference, e.g., comparison with a post-baseline value, the baseline value will be the last non-missing result prior to HSCT.

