Additional cell types and analytes for quantitative immunophenotyping include the absolute and relative numbers of CD3+CD19+ T cells (containing iC9), as well as the number of B cells, NK cells, and levels of IgA, IgM and IgG. In order to describe the pharmacodynamic effects of BPX-501 via proliferation of CD3+CD19+ cells, values post-rimiducid may be excluded. A separate analysis will examine CD3+CD19+ levels using the most recent samples available before and after treatment with rimiducid.

(v) *Time to immune reconstitution defined by CD3 count > 500 cells/uL; CD4 > 200 cells/uL or CD8 count of 200 cells/uL*

Time to immune reconstitution will be based on CD3, CD4 or CD8 counts for the defined thresholds above. Events are defined from the time of transplant to the time at which the threshold is achieved, with death considered as competing event. A patient not achieving the threshold T cell count will be censored on the last recorded visit day.

Time to immune reconstitution will be estimated using a Nelson-Aalen cumulative incidence function for each T cell subtype. Parameters estimates will be summarized for all subjects and by disease type (malignant or non-malignant). When estimable, additional summary statistics will include the median, minimum, maximum, the 25th and 75th percentiles of immune reconstitution, along with the number of events and censored observations. A cumulative incidence plot with descriptive summary statistics will be presented along with the number of patients at risk at various time points.

(vi) *Disease-Free/chronic GvHD-Free survival at 180 days*

The disease-free/chronic GvHD-free survival endpoint at 180 days will be assessed on the ITT (FAS) population. Events corresponding to disease-free/chronic GvHD-free survival outcomes include chronic GvHD, disease relapse for malignant subjects, disease recurrence for non-malignant subjects, or death by any cause. For patients with multiple events, the event that occurs first and the corresponding time will be used. Patients who do not experience an event will be censored on the last recorded visit day. Each patient outcome duration will be calculated from the date of transplant.

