Cumulative incidence of acute leukemia relapse will be estimated from time of transplant using a Nelson-Aalen cumulative incidence function and treating death prior to relapse as a competing risk. Cumulative incidence plots with descriptive summary statistics including incidence and 95% confidence intervals will be presented.

(ii) Time to Neutrophil Engraftment

Events for neutrophil engraftment is defined as the first of three consecutive measurements of an ANC $\geq 500/\mu\text{L}$ following the conditioning regimen induced nadir, starting from Day 0 (day of transplant). A patient that does not achieve the count of ANC $\geq 500/\mu\text{L}$ will be censored at the last assessment date.

Time to neutrophil engraftment will be estimated using a Nelson-Aalen cumulative incidence function. Death will be considered a competing event. Cumulative incidence plots with descriptive summary statistics including median engraftment time and 95% confidence intervals will be presented.

(iii) Time to Platelet Engraftment

Events for platelet engraftment is defined as the first of three consecutive measurements of platelet count $\geq 20,000/\mu\text{L}$ without platelet transfusion support for seven days. A patient that does not achieve the threshold platelet count of $\geq 20,000/\mu\text{L}$ as required will be censored at the last assessment date.

Time to platelet engraftment will be estimated using a Nelson-Aalen cumulative incidence function. Death will be considered a competing event. Cumulative incidence plots with descriptive summary statistics including median engraftment time and 95% confidence intervals will be presented.

(iv) Analysis of Primary and Secondary Graft Failure

Primary graft failure is defined as failure to achieve an absolute ANC ≥ 500 cells/ μ L by Day 30. The proportion of patients experiencing primary graft failure in the first 30 days will be summarized and reported with a 95% confidence interval.

Secondary graft failure is defined as initial neutrophil engraftment followed by a subsequent decline in neutrophil counts to < 500 cells/ μ L which is unresponsive to growth factor therapy. Sustained neutropenia, i.e., neutrophil counts to < 500 cells/ μ L, observed for greater than 30 days from the administration of growth factors will be summarized.

(v) Infectious Complications

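### A further transplant after BPX-501 is not a competing event for time to immune reconstitution (or, less so, engraftment), so recovery that follows it is counted for the index graft

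*SAP*

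**What the plan says.** SAP 6.4.2(v) analyses time to the CD3, CD4 and CD8 thresholds by cumulative incidence: "Events are defined from the time of transplant to the time at which the threshold is achieved, with death considered as competing event". The censoring rule is: "A patient not achieving the threshold T cell count will be censored on the last recorded visit day".

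SAP 6.4.3(ii) and (iii) repeat the structure for neutrophil and platelet engraftment. Each states "Death will be considered a competing event", and a patient who does not reach the count "will be censored at the last assessment date".

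Two sentences deal with multiple transplants. SAP 3.2: "If a patient received more than one HSCT, the time of the last HSC infusion immediately preceding infusion with BPX-501 will be the transplant date". SAP 6.2.3: "If a patient received multiple HSCTs, the date of HSCT which occurred immediately before administration of BPX-501 will be considered study Day 1". Both set the time origin, and both look back from BPX-501.

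The general dropout rule in SAP 6.2.2 is: "Patients will be censored at the time of their last documented study visit prior to or at the time of study withdrawal". Neither document makes graft failure, a further HSCT or another donor-cell infusion a withdrawal, a censoring point or a competing event.

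**The concern.** The curves are meant to describe recovery from the index graft supported by BPX-501. If that graft fails, or the disease relapses, and the patient is transplanted again while still below the threshold, later recovery comes at least partly from the new cells. Under the present rules the patient stays at risk, and the first crossing after the new transplant is an event. A failure of the index graft then appears in the curve as a late success.

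This matters because enhancing immune reconstitution is named in the SAP's primary objective (3.1) and time to reconstitution is a listed secondary endpoint (3.2(v)). The situation is foreseeable: SAP section 2 names graft failure, poor immune reconstitution and relapse as known limits of haploidentical transplantation, and 6.4.3(iv) defines primary and secondary graft failure.

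**Working it through.** **Step 1: what each rule covers.** The plan gives no figure for this point, so there is none to reproduce. The rules can be set side by side.

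| Situation | Rule in the SAP | Result |
|---|---|---|
| Re-transplant before BPX-501 | 3.2, 6.2.3 | Clock restarts at the new graft |
| Re-transplant after BPX-501, threshold already met | None needed | Event already counted, correctly |
| Re-transplant after BPX-501, threshold not met, crossed later | None | Event, timed from the index transplant |
| Transplanted, never given BPX-501 | 6.1 | Outside the ITT (FAS) population |

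Only the third row is a gap.

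**Step 2: which endpoints are exposed.** BPX-501 is given at day 14 ± 4, or under some protocol versions day 21 ± 14 (SAP 4.1). Secondary graft failure by definition follows neutrophil engraftment (6.4.3(iv)), so those patients are neutrophil events before any rescue. The neutrophil curve is therefore affected only by primary graft failure rescued after BPX-501. The T-cell thresholds carry most of the point.

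**Step 3: size.** Let g be the share of all patients rescued after BPX-501 while below the threshold, and q the share of those who then cross it. With everyone followed to day 180, the overstatement is the proportion of patients whose first crossing follows rescue. It is at most g, and about g × q apart from a few deaths. For g = 5% and q = 0.8: 0.05 × 0.8 = 4.0 points.

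A simulation shows the same with deaths included. None of its inputs on recovery, death or rescue is in the documents:
- N = 160, the efficacy-evaluable number in SAP 4.2, used only for scale; 200 replicates; Aalen-Johansen estimate at day 180.
- About 70% would reach the threshold by day 180 on the index graft in the absence of death; 5% die by day 180.
- Rescue on days 30-70 in a share g who do not recover on the index graft; a share q of these can cross 30-100 days later.

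| g (of 160) | SAP rule, q = 0.8 | Rescue competing, q = 0.8 | Difference, q = 0.8 | Difference, q = 0.5 to 1.0 |
|---|---|---|---|---|
| 2% (3.2) | 68.2% | 66.7% | 1.5 | 1.1 to 1.9 |
| 5% (8) | 68.9% | 65.0% | 3.9 | 2.3 to 4.9 |
| 10% (16) | 69.0% | 61.3% | 7.7 | 5.0 to 9.9 |
| 15% (24) | 69.6% | 58.2% | 11.4 | 7.2 to 14.7 |

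As the share of failed grafts rises from 2% to 15%, the SAP's curve does not fall, while recovery on the index graft drops from 66.7% to 58.2%.

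**Step 4: would censoring at rescue do?** No. In the same simulation, censoring gave 67.4% to 68.3% at every g and q. It treats a failed graft as if it could still recover at the rate of the others.

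**The case against.** **The documents do not show that this happens.** SAP 6.3.3 lists the number and type of prior HSCTs as baseline items, so the multiple-transplant rule may have been written only for earlier transplants. Stem-cell boosts and donor lymphocytes given after BPX-501 are mentioned nowhere. This stands as to size: the rate is unknown and may be small. It does not supply the missing rule.

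**Counting recovery regardless of later treatment is a legitimate choice.** It is, but the SAP does not say it has made that choice, and its other rules lean the other way. A re-transplant before BPX-501 restarts the clock. Platelet recovery must be free of transfusion support, and haemoglobin must be untransfused. CD3+CD19+ counts after rimiducid may be set aside. Relapse, a non-fatal event, competes with TRM/NRM in 6.4.2(i).

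**Graft failure is visible elsewhere.** A reader might infer that failed grafts disappear from the report. They do not: 6.4.3(iv) reports primary failure at day 30 with a confidence interval and defines secondary failure, and tables and listings of graft failures and HSCT infusions are planned. CD3+CD19+ counts also give a measure specific to the product. These outputs sit beside the recovery curves and do not correct them.

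**The BP-004 protocol, on which the SAP is based, is not among the documents.** If it withdraws patients at re-transplant, SAP 6.2.2 would censor them and the later crossing would not be scored. Failures would then not become successes, but Step 4 shows that censoring is not a sound substitute.

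**Conclusion.** The gap is real and the correction is specific. SAP 6.4.2(v), and to a lesser extent 6.4.3(ii)-(iii), credits the index graft with a first threshold crossing that follows a further transplant after BPX-501. The bias favours the treatment and is bounded, in practice, by the share of patients rescued before the threshold.

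Three stronger readings are not supported:
- That the table estimates the bias in this trial. It shows what would follow from assumed rescue rates; the documents give no rate.
- That all five thresholds are equally affected. The neutrophil endpoint is reached only through primary graft failure rescued after BPX-501.
- That the trial's main conclusion is at risk. The primary endpoint and the non-inferiority power case concern EFS at day 180 (SAP 3.2, 4.2, 6.4.1). The endpoints here are secondary or other efficacy analyses, and no test or decision rule is attached to them.

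**What to change.** In SAP 6.4.2(v) and 6.4.3(ii)-(iii), add after the sentence on death: *a further HSCT or other unmodified donor-cell infusion, given after BPX-501 and before the threshold is met, is a competing event at the date of that infusion.* Keep the death-only analysis as a sensitivity analysis, so that both readings are available.

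In 6.4.2(iv), do not simply drop T-cell counts after rescue. That would remove failed grafts from the later visits and leave a selected, better-recovering group. Flag these counts, show the visit summaries with and without them, and give the number of patients affected.

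The cost is one derived date and a few lines of text. HSCT dates should come from the data behind Listing 16.2.5.1; if any other donor-cell product was given, the SAP should name the source of its date. Reported incidences may be slightly lower.

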	Rimiducid Pharmacokinetics (PK): As achievable, blood samples will be drawn at the following time-points (in the same series as the split samples above): within 4 hours ( $\pm$ 30 minutes) prior to the initiation of rimiducid infusion; 30 mins ( $\pm$ 5 minutes) after initiation of the infusion; at 2 hours (< 5 min prior to end of the rimiducid infusion), 4 hours, 6 hours, 8 hours, 12 hours, and 24 hours ( $\pm$ 30 minutes) after the start of the infusion. (see Appendix F ).													

1 Peripheral blood (~12 mL, in green top tubes; as feasible for patient weight) shall be collected for Immune Reconstitution and clinical flow cytometry studies. The basic clinical flow panel includes CD3+ cells, (if achievable, alpha/beta CD3+ cells, gamma/delta CD3+ cells), CD4+ cells, CD8+ cells, Natural Killer cells, B cells, and CD3+/CD19+ cells, CD3+/CD19+/CD4+ cells and CD3+/CD19+/CD8+ cells. Additional flow panels may be included as deemed necessary by the treating physician. IgG, IgM and IgA levels shall be reported.

2 Vital signs include blood pressure, heart rate, respiratory rate and temperature.

3 Concomitant Medication: The protocol will be conducted during the routine clinical care of the patients. All treatments and critical medications, defined below shall be collected in the EDC database:

- Treatment for GVHD
- Prophylaxis and/or treatment for infectious complications
- Treatments in association with serious adverse events (SAE)s

Standard supportive care treatments, non-prescription medications/OTCs, NSAIDs, laxatives/stool softeners, vitamins, and herbal supplements will not be collected if they are not protocol-mandated.

4 Two purple top tubes (heparinized) of whole blood to be collected and frozen and then batch shipped to the Sponsor or designee per instructions in the laboratory manual for collection of the gene therapy monitoring.

5 For clinical assessment and management of neurotoxicity refer to [Appendix E](#).

6 GvHD assessments will be performed according to standard practice in the hospital. Refer to [Appendix A](#) and [Appendix B](#).

7 Research blood sample collection for rimiducid infusion to be sent as directed. Refer to [Appendix F](#) for collection and processing of samples for pPK testing.

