4.4. Clinical Assessments

Clinical and laboratory assessments were conducted at screening and on days 0, 14, 30, 60, 100 and 180. Patients received TCR $\alpha\beta$ T cell and CD19+ B cell depleted HSC on day 0. Unless otherwise protocol-specified, patients received the BPX-501 infusion on day 14+/- 4 days.

Clinical assessment, laboratory investigations, radiological investigations, and microbiological investigations will be conducted as per protocol schedule of assessments Table 1. Adverse events will be followed throughout the study period. In this study protocol, the scheduled study follow-up for each patient defined as 180 days. Further details of the schedule of assessments recorded on the electronic Case Report Form (eCRF) at each visit are provided in Table 1.

A full description of the study design, including inclusion/exclusion criteria, is provided in the study protocol.

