6.3.2. Protocol Deviations

Protocol deviations will be identified as major or minor through data reviews by the Sponsor prior to database lock. Descriptive statistics will be summarized for subjects with major protocol deviations with respect to the relevant analysis population. The summary may be grouped into different categories of major violations such as:

- Violation of inclusion/exclusion criteria
- Non-compliance with study procedures
- Inappropriate intake of prohibited concomitant medications
- Missing essential study visit assessments

- Lost to follow-up
- Administrative decision of investigator or sponsor

Multiple deviations can occur in the same subject and thus a subject may be counted in more than one deviation category.

Major and minor protocol deviations will be presented in a subject data listing for all enrolled population, sorted by site.

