The resolution of acute GvHD (aGvHD) or chronic GvHD (cGvHD) after administration of rimiducid will be based on the response grading of the GvHD criteria provided in the protocol. The event for this endpoint is any patient who achieved a best overall response (BOR, i.e., either a Complete Response (CR) or Partial Response (PR)) based on aGvHD grading. Only patients experiencing aGVHD who received rimiducid (AP1903) infusion for treatment will be considered for this endpoint. Best overall resolution of aGVHD is defined from the date of AP1903 infusion. The percentage of patients with acute or chronic GvHD, the number of doses of rimiducid, and the best overall response to rimiducid within 7 and 30 days will be presented in listings and summarized. Concomitant medication usage in subjects with acute or chronic GvHD and, further, among those subjects who went on to receive rimiducid, will also be summarized.

Additional analysis and summary statistics will be conducted for resolution of chronic GvHD after administration of rimiducid as well as any case of GvHD (acute or chronic).

(iv) Immune reconstitution as determined by T cell subset counts at day 180

- a. Median and range of CD3 counts at 30, 60, 100 and 180 days
- b. Median and range of CD4 counts at 30, 60, 100 and 180 days
- c. Median and range of CD8 counts at 30, 60, 100 and 180 days

Quantitative assessment of each immune T-cell counts will be performed at various visit time points after transplant as captured in clinical database up to day 180 of follow-up. Analysis and statistical summaries will be performed separately for each T cell subtype assessed. The pattern of each immune reconstitution lab counts will be summarized using graphical summaries and descriptive statistic summary tables including mean (standard deviation), median, and range (minimum, maximum) across the time points assessed. Plots of mean and median cell counts representing measurements over time will be generated to visualize general patterns over time of immune reconstitution.

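### Time to T-cell reconstitution censors non-achievers at the last visit rather than the last count, which can lower the estimate but never raise it

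*SAP*

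**What the plan says.** SAP section 6.4.2(v) sets a threshold for each of CD3, CD4 and CD8. On the event: "Events are defined from the time of transplant to the time at which the threshold is achieved, with death considered as competing event". On the estimator: "Time to immune reconstitution will be estimated using a Nelson-Aalen cumulative incidence function for each T cell subtype". On patients who stay below the threshold: "A patient not achieving the threshold T cell count will be censored on the last recorded visit day".

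Nothing in the item limits a visit to one at which the subset was counted. Section 6.2.2 does not help: its general rule for withdrawals also censors at the last study visit, and it leaves missing efficacy values unimputed. No sensitivity analysis for missing counts is specified for this endpoint.

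For two other endpoints defined by a blood count, neutrophil and platelet engraftment (section 6.4.3(ii) and (iii)), a patient who does not reach the required level "will be censored at the last assessment date".

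The planned timing of visits and counts is aligned. Section 4.4 says: "Clinical and laboratory assessments were conducted at screening and on days 0, 14, 30, 60, 100 and 180". Section 6.4.2(iv) summarises each subset on the later of those days, for example: "Median and range of CD3 counts at 30, 60, 100 and 180 days".

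**The concern.** Attending a visit does not show whether a child's CD4 count has crossed 200; only a CD4 count does. Suppose a child's last panel, at Day 60, is below threshold and the child then attends to Day 180 without another panel. Under the written rule this child is at risk and not reconstituted for 180 - 60 = 120 days in which crossing could not have been seen. The child adds to the denominator and cannot add an event. In effect, non-recovery is carried forward, which sits badly with the stated policy of not imputing.

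The same last-visit wording is used for disease-free/chronic GvHD-free survival in item (vi). It does less harm there, because relapse, chronic GvHD and death are events that clinical follow-up can pick up.

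At stake are the reconstitution curve, its median and quartiles, and the numbers at risk, which item (v) reports overall and by malignant or non-malignant disease. Enhanced immune reconstitution leads the primary objective in section 3.1, so these figures will be read closely even though the endpoint is secondary.

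**Working it through.** **Plan's own figure.** There is none to reproduce. The SAP gives no expected reconstitution rate, missing-count rate or target precision for this endpoint. All inputs below are therefore assumptions, except the count days 30, 60, 100 and 180 (sections 4.4 and 6.4.2(iv)).

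**Step 1: the mechanism by hand.** Take 100 patients, no deaths. By Day 60, 30 have reached the threshold and 70 have not. Of the 70, 14 attend to Day 180 with no further count. Of the 56 still counted, 28 reach the threshold by Day 180.
- Last-visit censoring (as written): 30% + 70% x 28/70 = 58%.
- Last-count censoring: 30% + 70% x 28/56 = 65%.

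The 7-point gap comes entirely from the 14 unmeasured patients. If all 70 had been counted, the two rules would agree.

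**Step 2: direction.** Let the unmeasured 14 recover at r times the rate of the measured (28/56 = 0.5). The true value is (30 + 28 + 14 x 0.5 x r)/100.

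| r | True value | Last-visit rule | Last-count rule |
|---|---|---|---|
| 0 | 58% | 58% | 65% |
| 0.5 | 61.5% | 58% | 65% |
| 1 | 65% | 58% | 65% |
| 1.5 | 68.5% | 58% | 65% |

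The written rule is correct or too low in every row. Last-count censoring is exact only at r = 1, and is too high when unmeasured patients recover more slowly.

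**Step 3: size at Day 180.** Let F(t) be the true proportion at or above threshold by day t. Ignore deaths, let recovery persist once reached, and let missing counts be unrelated to recovery. If a share m of the cohort has no count after day c but attends to Day 180, the written rule estimates F(c) + (1 - m) x [F(180) - F(c)]. The bias is therefore -m x [F(180) - F(c)].

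With log-normal times, F(t) = Phi(ln(t/median)/0.8):

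| Median | F(60) | F(100) | F(180) | F(180) - F(60) | F(180) - F(100) |
|---|---|---|---|---|---|
| 90 days | 0.31 | 0.55 | 0.81 | 0.50 | 0.25 |
| 120 days | 0.19 | 0.41 | 0.69 | 0.50 | 0.28 |

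Understatement in percentage points:

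| m | Day 100 and Day 180 counts both missing | Only Day 180 count missing |
|---|---|---|
| 0% | 0 | 0 |
| 5% | 2.5 | 1.3 to 1.4 |
| 15% | 7.5 | 3.8 to 4.3 |
| 30% | 15 | 7.6 to 8.5 |

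**Step 4: sensitivity to the pattern of missingness.** A second calculation lets a fraction of the patients still below threshold stop being counted after each count day while they keep attending. The assumed chance of first crossing at the four counts ranges from 5/15/25/40% to 20/40/50/60%, with death at 0% or 2% per interval. The loss at Day 180 is 5.6 to 6.6 points at a fraction of 5%, and 11.0 to 12.7 points at 10%. These figures exceed those in Step 3 because the fraction applies again after each count and only to patients not yet recovered. They do not contradict Step 3. They show that no single size can be quoted without the missing-count data.

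**The case against.** The strongest reply is that the two rules may give the same answer. They differ only for a patient who attends after the final count. A skipped panel followed by a later one does not matter, and the SAP schedules laboratory work with the visits. In the BP-404 follow-up, immune reconstitution is also sampled at every scheduled visit from month 9 to month 24. This stands: a reader might infer that reconstitution *is* understated, but the documents support only that it *can be*.

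A reader might also infer that missing panels are to be expected, above all in the smallest children. The protocol's Table 1 footnote reads: "Peripheral blood (~12 mL, in green top tubes; as feasible for patient weight) shall be collected for Immune Reconstitution". That qualifies the volume of a sample that is otherwise required, and it belongs to BP-404, whose schedule starts at month 9. It says little about Days 60 to 180. The SAP's deviation category "Missing essential study visit assessments" is one item in a generic list. Nothing links missing counts to body size or says they differ between malignant and non-malignant patients, so a spurious contrast between disease groups cannot be claimed.

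The engraftment comparison is suggestive only: the wording there does not name the neutrophil or platelet count either.

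Part of the remedy is already planned. Section 6.2.1 calls for the number of observations for continuous endpoints, and section 6.4.2(iv) summarises the counts by visit. Those summaries do not depend on the censoring rule and would reveal missing panels.

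Finally, last-count censoring has its own assumption, as Step 2 shows. None of this removes the defect in the written rule; it limits what can be said about its size.

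**Conclusion.** The concern holds conditionally. As written, the rule counts unmeasured time as event-free, so its effect on the cumulative incidence of reconstitution is downward or nil. The effect is nil if every non-achiever's last visit carries a count of the subset.

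Otherwise, at Day 180 it is about 0.50 x m when a share m has no count after Day 60, and about 0.25 to 0.28 x m when only the Day 180 count is missing. Both rest on the assumed log-normal times, on missing counts unrelated to recovery, and on ignoring deaths; m itself is not in the documents.

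A reader might take this as a threat to the trial's main result. It is not: the primary endpoint is event-free survival, which does not use this rule. The affected endpoint is secondary, descriptive and single-arm, and any error runs against BPX-501. It is still worth correcting, because the rule is explicit, its error has a known direction and the change is small.

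**What to change.** Replace the censoring sentence in SAP section 6.4.2(v) with: *A patient not achieving the threshold will be censored at the date of the last available count of that T-cell subset.* Apply it separately to CD3, CD4 and CD8, and keep death as a competing event.

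Report, for each subset, how many patients have a last visit later than their last count. If that number is zero, the question is closed. Keep last-visit censoring as a sensitivity analysis: last-count censoring is unbiased only if missing counts are unrelated to recovery, and the written rule shows the result if no unmeasured patient recovered.

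The cost is one sentence, one extra count per subset and one repeat run. Where counts are missing, slightly fewer patients remain at risk at late time points and the intervals there widen slightly. Where none are missing, the results do not change.
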